### III. General Investigational Plan

This within-subject, double-blind, placebo-controlled study will assess the analgesic effects of a range of cannabidiol (CBD) doses (0, 200, 400, or 800 mg, po). Normal, healthy volunteers with no current pain or substance use will participate in 4 outpatient laboratory sessions over the course of 4 weeks during which the analgesic effects of CBD will be assessed using the Cold-Pressor Test (CPT), a laboratory model of pain which has predictive validity for the clinical use of analgesics. The order of CBD dose will be counter-balanced across participants; **Table 1** illustrates a representative dosing schedule. Secondary measures will include subjective and physiologic effects of CBD, and the CPT, subjective mood and drug effects, and vital signs will be measured before and at specified time points after CBD administration. Determining the efficacy of CBD in an experimental model of pain will provide important endpoints (i.e., dose, time course) of this effect to further investigate the potential role for clinical use of CBD as an analgesic.

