**Table 1. Representative Dosing Schedule**

Day	M	T	W	Th	F
Week 1	Subject 1	Subject 2	Subject 3	Subject 4	Subject 5
Session	1	1	1	1	1
CBD (mg)	0	200	400	800	0
Week 2	S1	S2	S3	S4	S5
Session	2	2	2	2	2
CBD (mg)	200	400	800	0	200
Week 3	S1	S2	S3	S4	S5
Session	3	3	3	3	3
CBD (mg)	400	800	0	200	400
Week 4	S1	S2	S3	S4	S5
Session	4	4	4	4	4
CBD (mg)	800	0	200	400	800

Based on CBD's long half-life (21-33 hrs) (Consroe et al., 1998), sessions will be separated by at least 5 days to allow for CBD clearance and prevent carryover effects. Physiological effects (heart rate and blood pressure) and side effects will be monitored throughout the session.

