### **Laboratory Sessions and Cold Pressor Test (CPT):**

In the current study, there will be four laboratory sessions to assess the effects of a range of cannabidiol doses on analgesia. During the CPT test sessions, which will start and end at approximately 0900 and 1630hr, the analgesic, subjective, and physiological effects of cannabidiol will be determined repeatedly following a pretreatment of cannabidiol or placebo (see **Table 3**). Administration of cannabidiol will occur at 1000 hr. Baseline assessments will include measurements of analgesia (CPT), mood, blood pressure and heart rate. A breathalyzer test will be done before each session and urine samples will be tested for illicit drug use and, for women, pregnancy (prior to all sessions). Participants testing positive for drugs will be excluded from further participation. A light breakfast will be provided before CBD administration (e.g., bagel, juice, coffee).

The CPT, a well-established model for producing pain in humans (e.g., Chen et al., 1989; Conley et al., 1997; Zacny et al., 1996), will be performed once before and six times after drug administration and will last approximately 15 minutes. Our laboratory and others have shown that multiple CPTs can be carried out within the same day with little or no carryover effects between tests (e.g., Conley et al., 1997; Zacny et al., 1996), and it can be used to detect the analgesic effects of cannabinoids (Cooper et al., 2013). In this assay, the two dependent measures are latency to feel pain and latency to withdraw the hand from the cold water. Because previous research has shown that experimenters of the opposite sex influence responding to painful stimuli (Clark and Goodman, 1974; Clark and Mehl, 1971; Levine and De Simone, 1991), the sex of the experimenter will always be of the same sex as the research participant.

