*Laboratory Facility:* All experimental sessions will be conducted in the Substance Use Research Center (SURC) located on the 3rd floor of the NYS Psychiatric Institute. Participants will sit in a comfortable task chair in front of a Macintosh computer. A response manipulandum (“mouse”) will be used for completion of pain rating scales and subjective-effects questionnaires.

**Table 2.** Session Schedule

Time (hr)	TIME (min)	EVENT
0900	-60	Urine, breathalyzer, breakfast
0930	-30	Baseline assessments: Mood scales, CPT
1000	0	Solution administration
1030	30	BP/HR, SRF, Mood scales
1100	60	SRF, Mood scales, CPT
1130	90	BP/HR, SRF, Mood scales
1200	120	SRF, Mood scales, CPT
1230	150	BP/HR, SRF, Mood scales
1300	180	SRF, Mood scales, CPT
1330	210	BP/HR, SRF, Mood scales, Lunch
1400	240	SRF, Mood scales, CPT
1430	270	BP/HR, SRF, Mood scales
1500	300	SRF, Mood scales, CPT
1530	330	BP/HR, SRF, Mood scales
1600	360	SRF, Mood scales, CPT
1615	375	BP/HR, SRF, Mood scales
1630	390	BP/HR, Field Sobriety Test, participant discharge

**Table 3.** Events Occurring During the Cold-Pressor Test

TIME (sec)	EVENT
-190	ST, Warm tank immersion, State
-10	ST, Vital Signs
0	Cold water immersion
180 or When hand is withdrawn	ST, Vital Signs, Pain Intensity/Bothersomeness Scales, CPT-VAS, SF-MPQ, State

*ST=skin temperature      Vital signs=blood pressure and heart rate      CPT-VAS=Visual Analog Scales  
 State=State Anxiety Inventory      SF-MPQ=Short-Form McGill Pain Questionnaire\**

*\*See descriptions of questionnaires above.*

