**STATSTICAL ANALYSIS PLAN**

Repeated measures analysis of variance (ANOVA) with planned comparisons were used to assess cannabidiol’s dose-related effects on measures of pain and subjective drug effects associated with abuse liability. For each participant under each dose condition, pain threshold and tolerance were calculated as the difference from baseline CPT (pre-drug administration) values. Subjective pain ratings (Pain Intensity and Bothersomeness Scales) were also measured as a function of change from the baseline response. Changes scores from each of the three active cannabidiol dose strengths were compared to placebo (i. e., 0 mg vs 200 mg; 0 mg vs 400 mg; 0 mg vs 800 mg) for each of the measures specified above. Results were considered statistically significant when *p* values were equal to or less than 0.01 using Huynh-Feldt corrections (SuperANOVA, Abacus Concepts, Inc., Berkley, CA).

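### Subtracting a single pre-dose cold-pressor test costs power in the dose-versus-placebo contrasts, by an amount that depends on a within-participant correlation the documents do not give

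*Combined protocol and SAP*

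**What the plan says.** The General Investigational Plan sets the design: "This within-subject, double-blind, placebo-controlled study will assess the analgesic effects" of four dose conditions, one per session, in 18 participants. In each session the cold-pressor test (CPT) "will be performed once before and six times after drug administration". Table 2 (Session Schedule) puts the single pre-dose test at -30 minutes: "Baseline assessments: Mood scales, CPT".

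The Statistical Analysis Plan states that "pain threshold and tolerance were calculated as the difference from baseline CPT (pre-drug administration) values". The pain intensity and bothersomeness ratings "were also measured as a function of change from the baseline response". Each active dose is compared with placebo in a repeated measures ANOVA with Huynh-Feldt correction, and a result is significant when p "values were equal to or less than 0.01". No covariate is named. The plan does not say whether the six post-dose tests are averaged or kept as a time factor, although the General Investigational Plan expects that the study "will provide important endpoints (i.e., dose, time course) of this effect".

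On washout, the Medication section gives a half-life of 21-33 hours and says that "sessions will be separated by at least 5 days to allow for CBD clearance and prevent carryover effects". The documents give no pre/post correlation, SD, effect size or target power, and state N=18 without a calculation.

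**The concern.** In a parallel-group trial, subtracting the baseline removes stable differences between people. Here every participant receives every dose, so those differences drop out of each contrast anyway. Subtraction can then only remove session-to-session shifts within a person, and it pays for that by adding the noise of one unreplicated test. The efficient slope on the pre-dose value is the within-participant session correlation r; the change score forces it to 1.

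With 18 participants and a 0.01 threshold, precision largely decides whether a real dose effect is detected. The baseline is already collected, so any gain needs no new data.

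**Working it through.** The documents contain no power figure to reproduce, so r is varied as an assumption.

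**Inputs.** From the documents: N=18, four sessions each, one pre-dose and six post-dose tests, three contrasts with placebo, threshold 0.01. Assumed: two-sided testing, normal data, equal variances and correlations across tests, no dropout, and Table 1's four orders split 5/5/4/4.

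**Variances.** Let a session effect have variance v and single-test noise have variance 1, so r = v/(v+1). For the difference between two doses in one participant:
- Change score, six-test mean: 2(1 + 1/6). One time point: 2(1 + 1).
- Covariate model, six-test mean: 2(v + 1/6 - v²/(v+1)). One time point: 2(v + 1 - v²/(v+1)).

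The ratio of change score to covariate model is 7/(6r+1) for the six-test mean and 2/(1+r) for one time point.

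**Power.** Error df are 72 - 18 - 3 = 51 for the change score and 50 with the covariate; critical t is 2.676 and 2.678. For the six-test mean the change-score SE is √(2 × 1.167/18) = 0.360, so 50% power needs an effect of about 0.360 × 2.676 = 0.96 single-test noise SDs. For one time point it is √(4/18) × 2.676 = 1.26. Charging a factor (1 + 1/49) for estimating the slope, the covariate SE at r=0.5 (v=1) is √(2 × 0.667/18 × 1.020) = 0.275. The expected t is 0.96/0.275 = 3.49, or about 79% power; simulation gives 78%.

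| Assumed r | 0.2 | 0.5 | 0.8 | 0.9 |
|---|---|---|---|---|
| Variance ratio, six-test mean | 3.18 | 1.75 | 1.21 | 1.09 |
| Covariate power, change score at 50% | 97% | 78% | 59% | 54% |
| Variance ratio, one time point | 1.67 | 1.33 | 1.11 | 1.05 |
| Covariate power, change score at 50% | 77% | 65% | 54% | 51% |

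Without carryover, the simulated false-positive rate of the covariate model is 0.8-1.1%. Its advantage is gone when the ratio equals (1 + 1/49)(2.678/2.676)² = 1.022, which is r = 0.975 (six-test mean) or 0.957 (one time point). Below r=0.5 the change score is less precise than ignoring the baseline altogether.

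**Which r.** It is the correlation of session deviations within a participant, not the raw correlation across people. If 70% of single-test variance were between participants (assumed), a within-participant r of 0.5 would appear as a raw correlation of 0.7 + 0.3 × 0.5 = 0.85.

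**Dose-by-time.** The same pre-dose value is subtracted from all six tests in a session, so it cancels from every difference between time points.

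**Carryover.** In Table 1, 800 mg is only ever followed by placebo, in three of the four orders, or 13 of 18 participants under the assumed split. Suppose the shift is common to that session's pre- and post-dose tests. The change score cancels it. The covariate model keeps a fraction of about (1 - r), which biases the active-versus-placebo contrast downwards.
- Shift of 0.5 noise SD (assumed): bias is about 0.5 × 13/18 × (1 - r) = 0.29/0.18/0.07 at r = 0.2/0.5/0.8. Simulated covariate power is about 71/57/51% against 50%, and false positives about 10/2.5/1%.
- Shift of 0.5 full within-participant SD, √(v+1) (assumed): false positives are about 13/4.5/2%. Bias is about 0.361 × √(1 - r) = 0.32/0.26/0.16, leaving an expected t of about (0.96 - bias)/SE = 0.64/0.204, 0.70/0.275, 0.80/0.331 = 3.1/2.5/2.4 against 2.678. At r = 0.5 and 0.8 power then falls below the change score's 50%.
- Shift proportional to drug remaining (assumed): at 5 days 2^(-120/33) = 8.0% to 2^(-120/21) = 1.9% of a dose is left, so a 0.96-SD effect leaves at most 0.96 × 0.080 = 0.08 SD. Covariate power is about 96/76/58%.

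In every carryover case the change score's false-positive rate stays near 1%.

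**The case against.** The strongest reply is that the plan contains no error. The change score is a valid, unbiased analysis, and choosing a covariate instead is a matter of efficiency. That is right, and the point claims no more. The reply also notes that the size rests entirely on an unknown r. The largest figures belong to the six-test mean, which the plan does not specify, and at one time point the gain is only about 4 percentage points at r=0.8. That stands too.

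The carryover argument has real force. Under the representative schedule, any residual 800 mg effect falls on the comparator of all three contrasts, and the change score protects against it better. A reader might infer that the covariate model is better throughout, or that a comparison of pre-dose values by preceding dose could decide which result to believe. Neither follows. Large carryover can remove or reverse the gain. The check would flag a 0.5 noise-SD carryover at the 0.05 level in only 16/11/8% of trials at r = 0.2/0.5/0.8, and choosing a result on that basis has an unexamined error rate. The washout figures make large carryover less likely, but only if effect tracks the amount of drug left, which the documents do not establish.

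Finally, a session-varying covariate is a different model from a Huynh-Feldt repeated measures ANOVA. The six-test mixed model and the session-mean model give the same overall dose contrast only with complete data, and Criteria for Early Discontinuation allows a CPT to be suspended for the day.

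**Conclusion.** The point holds as a minor one about efficiency. Subtracting a single pre-dose test inflates the variance of the dose-versus-placebo contrasts by 7/(6r+1) for a six-test mean or 2/(1+r) at one time point. That is substantial at r of 0.5 or below, modest at 0.8 and negligible from about 0.9. These figures assume normal data, equal variances and correlations, two-sided testing and no carryover; the documents do not allow r to be fixed.

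Three stronger readings are not supported. A reader might infer that the planned tests are biased or inflate type I error; they do neither. A reader might infer that a null result here would be due to the baseline handling; without r, an SD or an effect size, that cannot be said. A reader might infer that the time-course analysis is weakened; the dose-by-time interaction is unaffected.

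**What to change.** If results are not yet known, prespecify the post-dose value as the outcome, with participant, dose and the within-participant deviation of the session's pre-dose CPT as terms. Keep the three contrasts and the 0.01 threshold. If all six tests are modelled, add time, dose-by-time and a participant-by-session random effect, and state how incomplete sessions are handled. Always report the change-score analysis as a fixed sensitivity analysis. Tabulate pre-dose CPT by preceding dose for description only, and do not choose between the two results from the data.

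The Statistical Analysis Plan is written in the past tense. If results are already known, keep the change score as primary and add the covariate model as a labelled sensitivity analysis; this recovers no power for the primary result but shows how far it depends on one noisy test.

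The cost is SAP wording, a standard mixed model, one degree of freedom (51 to 50, and about 2% of variance), and weaker protection against carryover than the change score gives.

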**Criteria for Early Discontinuation:**

Throughout participation, we will carefully monitor participants for medication tolerability. The research team will continually assess the participant’s health throughout the testing sessions and will remove participants from the study if physical or mental deterioration is observed.

The CPT has been associated with cardiovascular effects that include increases in heart rate and blood pressure. The participants will be monitored before, during, and after the CPT. Blood pressure and heart rate will be measured both before and after the test. In the past, we have found the CPT to produce about a 10-point increase in systolic and diastolic pressure (Kowalczyk et al., 2006). Participants will be informed of the cardiovascular risks associated with the test, and medical personnel will be on staff during the test in the case of an emergency. Participants may experience transient elevations in systolic and diastolic blood pressure as well as heart rate in response to cold-water immersion. A systolic blood pressure of greater than 180 or a diastolic blood pressure greater than 110 (each measure confirmed by manual reading), in which either is sustained for more than 120 sec., will result in suspending the cold pressor test for that participant for that given day. In addition, a single reading of systolic blood pressure greater than 200, or a single reading of diastolic pressure greater than 120 (each measure confirmed by manual reading), or a confirmed heart rate of greater than 160, will result in suspending the cold pressor test for that participant for that given day. If any of these parameters is exceeded, we will immediately confer with a staff internist to determine whether the episode of hypertension or tachycardia is resolving and can be followed up on an outpatient basis, or whether acute medical intervention is indicated. Under these conditions, the cold pressor test will not be administered again until consultation is sought and the IRB is alerted and approval is obtained for continuation of testing with that participant. If these changes are observed on a second occasion, the CPT will not be administered again to that participant.

Additionally, immediate removal from the study will result if significant adverse reaction to the study drug or assessment procedure is noted. Upon removal of a participant from the study, he or she will be provided with the appropriate follow-up treatment by a study physician or a research nurse. We anticipate, however, that careful screening, informed consent, dose selection, and participant monitoring, will obviate the need for such emergency care. We have been conducting inpatient and outpatient clinical pharmacology research for over 15 years and have encountered no serious adverse incidents.

*MAJOR RISKS:*

**1) Cannabidiol:** Participants are informed of possible side effects following CBD administration. The medication has few psychoactive effects (e.g., Leweke et al., 2000; Fusar-Poli et al., 2009), although there is a report of decreased anxiety and increased sedation (400 mg; Crippa et al., 2004). One placebo-controlled study administered CBD (approximately 700 mg/day) to patients with Huntington's disease for 6 weeks and reported no significant adverse effect from the medication relative to placebo (Consroe et al., 1991). CBD doses up to 1500 mg/day have been given for several weeks to schizophrenic patients with no side effects reported (Zuardi et al., 1995, 2006). Cannabidiol exposure may have a harmful effect on a fetus or a newborn, thus individuals will not be allowed to participate in the study if they are pregnant or breastfeeding, or if they cannot use an appropriate contraception method.

**2) Pain procedure (Cold Pressor Test):** During the CPT there may be significant discomfort associated with the stimuli. However, pain dissipates rapidly after removal of the extremity from the cold water. Except for the acute stress associated with the pain test, there have been no known

long-term consequences of these procedures. Participants who are unable to tolerate the procedures during the training session will not be enrolled in the study.

Participants will be monitored continuously throughout the experimental procedure. Emergency medical equipment is available in our laboratory, which is located in a hospital where a full medical emergency back-up team is constantly available. As stated above, (page 10), the CPT is associated with cardiovascular changes that include elevations on heart rate and blood pressure. If systolic blood pressure of greater than 180 or a diastolic blood pressure greater than 110 (each measure confirmed by manual reading), in which either is sustained for more than 120 sec. is observed the CPT for that participant will be suspended for that given day. In addition, a single reading of systolic blood pressure greater than 200, or a single reading of diastolic pressure greater than 120 (each measure confirmed by manual reading), or a confirmed heart rate of greater than 160, will result in suspending the CPT for that participant for that given day. If any of these parameters is exceeded, we will immediately confer with a staff internist to determine whether the episode of hypertension or tachycardia is resolving and can be followed up on an outpatient basis, or whether acute medical intervention is indicated. If these changes are observed on a second occasion, the CPT will not be administered again to that participant.

**3) Blood drawing:** Blood drawing during the screening process may cause mild discomfort at the site where the needle is inserted, and it poses a small risk of bruising at the site as well as an extremely low risk of infection. A total of 15 ml of blood will be drawn throughout the 4-session study; we will do complete blood chemistry and a plasma pregnancy test during screening (15 ml).

*INSTRUMENTS USED:*

Prescreening and Screening Assessments: Measures used to initially characterize participants include personal questionnaires, medical history, physical examination, laboratory assessments of blood and urine, and body weight. In addition, females will be administered a serum pregnancy test (beta HCG). A detailed list of screening measures is shown below:

- Telephone Interview: 10 min. (Appendix 3)
- Intake and Drug History Questionnaire: 10 min. (Appendix 4)
- General Health Questionnaire: 5 min. (Appendix 5)
- Medical History Questionnaire: 10 min. (Appendix 6)
- Michigan Alcoholism Screening Test: 5 min. (Appendix 7)
- Beck Depression Inventory: 5 min. (Appendix 8)
- Race and Ethnicity Questionnaire: 1 min. (Appendix 9)
- Trauma Assessment for Adults – Self-Report: 5 min. (Appendix 10)
- Yale PRIME Screening Test: 5 min. (Appendix 11)
- Vocabulary Assessment: 5 min. (Appendix 12)
- Fagerstrom Test of Nicotine Dependence: 5 min. (Appendix 13)
- Personal and Drug History Interview: 30 min. (Appendix 14)
- Mini-SCID Assessment: 30 min. (Appendix 15)
- Physical and Psychiatric Examination: 30 min. (Appendix 17-18)
- Laboratory and Hospital Tests: 1 hr.

Study Session and CPT

- A. Solution Rating Form (Appendix 19)
- B. Visual Analog Scale – WAS (Appendix 21)
- C. State Anxiety Questionnaire (Appendix 20)
- D. 11-point Lichert pain intensity scale (Appendix 23)
- E. Cold Pressor Test-Visual Analog Scale (CPT-VAS) (Appendix 22)
- F. Short Form-McGill Pain Questionnaire (SF-MPQ) (Appendix 24)

Safety Measures

- A. Vital signs including heart rate, systolic and diastolic blood pressure, oral body temperature, respiratory rate (10 minutes)
- B. Physical Examination (30 minutes)
- C. Laboratory Chemistries (15 minutes)
- D. ECG (20 minutes)
- E. Urine Toxicology (for drugs of abuse) (5 minutes)
- F. Adverse Events Assessment (5 minutes)

[name]  
NCT #02751359  
02/23/21
